***Please enter the Short Title you would like to use to reference the study:**

1:1 Pocket Colposcope in Kenya

* This field allows you to enter an abbreviated version of the Study Title to quickly identify this study.

Document Date: 05/03/2024

NCT04998318

Standard Research Summary

Purpose of the Study

- Objectives & hypotheses to be tested

Primary

1. Compare the performance of the Pocket colposcope to Visual Inspection with Acetic Acid (VIA) and Visual Inspection with Lugol's Iodine (VILI) for detection of precancerous lesions among HPV+ women in Kenya.
2. Determine sensitivity, specificity and positive/negative predictive values of different triage strategies for HPV+ women.

Secondary

1. Analyze patient and provider pre-exam surveys to address possible obstacles in routine cervical cancer screening and build awareness.
2. Analyze patient and provider post-exam surveys to gather their perspective on use of Pocket system.

Tertiary

1. Use the de-identified colposcopy images to test our automated algorithm named CARE. This is a retrospective analysis for modeling and development of the algorithm, not guiding clinical care. The addition of the cellphone camera images will help facilitate this algorithm.

Background & Significance

- Should support the scientific aims of the research

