Pocket Colposcope images will be evaluated 1) at the time of the initial exam, 2) by expert colposcopists and, 3) by our image processing algorithm [12]. Provider impression of the Pocket Colposcope images, provider impression of the standard-of-care VIA/VILI and the algorithm output will be compared against pathology. The diagnostic information gained will be used to determine the sensitivity and specificity of the algorithm. Specifically, the two-sided McNemar's test will be used to determine statistically significant differences in specificity and sensitivity for each comparison 1) VIA/VILI impression vs. Pocket-provider impression during the exam, 2) expert provider interpretation vs. Pocket--algorithm-based results post-study and 3) VIA/VILI and Pocket Colposcopy based impressions (during exam) vs. algorithm-based results (post- study) to test our hypothesis that provider based interpretation of the Pocket images and the algorithm perform significantly better than VIA/VILI, and that the automated algorithm performs comparably to an expert. To obtain a better understanding of the performance of the three tests, we will carry out a standard and weighted Kappa to look at the agreement between tests and the impact of disease severity on agreement. The literature suggests that approximately 20% of the patients from each arm will have a CIN2/3 diagnosis.

Data & Safety Monitoring

- Summarize safety concerns, and describe the methods to monitor research subjects and their data to ensure their safety, including who will monitor the data, and the frequency of such monitoring. If a data monitoring committee will be used, describe its operation, including stopping rules and frequency of review, and if it is independent of the sponsor (per 45 CFR 46.111(a) (6)).

All data will be obtained at the sites in Kenya. The Duke team will be in communication with local PIs/CRCs to ensure the images and data are uploaded correctly. Data monitoring will be conducted on a routine basis by the PI and study team as specified below in Section 13. As necessary, the PI will make source documentation and protocol data available to appropriate regulatory agencies, which may include but is not limited to the DCI Monitoring Team, the DCI Cancer Protocol Committee, the DUHS IRB, the Duke University SOM's Office of Regulatory Affairs and Quality (ORAQ) and the National Cancer Institute.

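### The plan has no primary accuracy measure and no rule joining sensitivity and specificity, so four separate tests could each be cited as superiority over VIA/VILI

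*Combined protocol and SAP*

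**What the plan says.** In Data Analysis & Statistical Considerations, "the two-sided McNemar's test will be used to determine statistically significant differences in specificity and sensitivity for each comparison". Three comparisons are listed:

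- "1) VIA/VILI impression vs. Pocket-provider impression during the exam"
- "2) expert provider interpretation vs. Pocket--algorithm-based results post-study"
- "3) VIA/VILI and Pocket Colposcopy based impressions (during exam) vs. algorithm-based results (post- study"; this one contains two contrasts.

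The stated purpose is "to test our hypothesis that provider based interpretation of the Pocket images and the algorithm perform significantly better than VIA/VILI", and also "that the automated algorithm performs comparably to an expert".

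The section gives no significance level, primary measure, test order, multiplicity rule or limit on loss in the other measure. Under Purpose of the Study, the first primary objective compares the performance of the Pocket device with VIA and VILI without naming a measure. The second lists sensitivity, specificity and both predictive values without ranking them. The algorithm is a tertiary objective, described thus: "This is a retrospective analysis for modeling and development of the algorithm, not guiding clinical care".

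**The concern.** Sensitivity and specificity trade off. A reader who calls more lesions gains sensitivity and loses specificity without telling diseased from healthy any better. If superiority may rest on one of the two measures, a change in calling habit can be reported as a better device. The reverse shift could be reported as better specificity while disease is missed.

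This matters here because Background & Significance asks for a second test that both finds disease and prevents overtreatment. Both measures have to count, yet the analysis has no rule that joins them. Separately, several tests that could each support the same headline raise the chance of a false one. Putting a tertiary algorithm into the primary hypothesis adds to their number.

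**Working it through.** The plan states no alpha, power, expected accuracy or error rate, so there is no figure to reproduce.

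**Inputs from the documents.** 1056 women randomized 1:1, so 528 per arm (Design & Procedures). About 20% CIN2/3 per arm (Data Analysis), so 528 × 0.20 = 105.6, about 106 cases, and about 422 non-cases per arm. Subject Recruitment instead gives a total of 400, which means 40 cases and 160 non-cases per arm.

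**Assumptions.** Two-sided 5% level, hence 2.5% in the favourable direction; all starting accuracies; an equal-variance binormal ROC curve; unpaired comparison, because the arms contain different women.

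**Counting tests.** Comparison 1: 1 contrast × 2 measures = 2. Comparison 2: 2. Comparison 3: 2 contrasts × 2 = 4. Total 8. Tests that involve VIA/VILI: Pocket provider (2) and algorithm (2) = 4.

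**False favourable result in at least one of the 4.** If independent, 1 − 0.975^4 = 9.6%. A simulation with a shared VIA/VILI arm and correlation of 0 to 0.7 between the two Pocket-arm readings gives 8.9% down to 7.4%. With the provider contrast alone (2 tests), 1 − 0.975^2 = 4.9%.

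**Threshold shift.** Start at 60% sensitivity and 75% specificity: d′ = z(0.60) + z(0.75) = 0.253 + 0.674 = 0.928. At a new sensitivity s on the same curve, specificity = Φ(0.928 − z(s)). The chance of a significant difference is Φ(|p2 − p1|/SE − 1.96), with SE = √{[p1(1 − p1) + p2(1 − p2)]/n}.

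| Shift in sensitivity | New sensitivity / specificity | Sensitivity significantly better (106 cases) | Specificity significantly worse (422 non-cases) | Sensitivity significantly better (40 cases) |
|---|---|---|---|---|
| 5 points | 65% / 70.6% | 11% | 30% | 7% |
| 10 points | 70% / 65.7% | 33% | 85% | 15% |
| 20 points | 80% / 53.4% | 90% | over 98% | 52% |

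For the 20-point row, SE = √[(0.24 + 0.16)/105.6] = 0.0615, 0.20/0.0615 = 3.25, and Φ(3.25 − 1.96) = 0.90. With 160 non-cases the specificity loss in that row is still significant over 98% of the time.

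Per 1,000 women at 20% CIN2/3, the 20-point shift means 200 × 0.20 = 40 more detections and 800 × (0.75 − 0.534) ≈ 173 more false positives. Positive predictive value falls from 120/(120 + 200) = 37.5% to about 160/(160 + 373) = 30%.

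**Other starting points.** From 60/80, 70/70 and 50/85, with shifts of 0.2 to 0.6 SD, the chance of significantly better sensitivity is 0.19 to 0.93 at 1056 women and 0.10 to 0.55 at 400. In the opposite direction from 60/80, a 0.4 SD shift raises specificity to 89.3% (significantly better with probability 0.96) while sensitivity falls to 44.2%.

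**The case against.** Several stronger readings are tempting, and the documents do not support them.

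- A reader might infer that any one significant test suffices. The plan does not say so. The hypothesis joins provider and algorithm with an *and*, and the tests cover both measures. If success were required on all of them, multiplicity would not inflate the claim. But the plan does not state that rule either. If *and* only means that both readers must succeed on some measure, the threshold route stays open.
- A reader might count all 8 tests and quote 1 − 0.95^8 = 34%. That includes four tests that cannot show anything against VIA/VILI, and it counts unfavourable results.
- A reader might call the testing wholly unordered. Purpose of the Study does rank Pocket against VIA/VILI as primary and the algorithm as tertiary. What is missing is that ranking in the analysis, and any order between sensitivity and specificity.
- A reader might infer that a rise in false positives would go unseen. It would usually not: specificity is tested too, and a large loss would almost certainly be significant. The risk lies in how a mixed result is interpreted.

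It is also fair to say that a lower threshold under magnification is conjecture. The Background attributes VIA's diminished sensitivity to lack of magnification, and expects added glycogen or vascular features to help both measures. The 90% belongs to a large assumed shift; at 5 points it is 11%. These objections limit the size of the concern but do not supply the missing rule.

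**Conclusion.** The point holds as a gap in the success rule. With four tests against VIA/VILI, the chance of at least one falsely favourable result is about 7% to 10% rather than 2.5%, if one result is allowed to carry the claim. The threshold shift is the weightier part: 11% to 90% for shifts of 5 to 20 points on the assumed curve with 106 cases per arm, and 7% to 52% with 40. These figures rest on a 5% level, assumed accuracies, a binormal curve, 20% CIN2/3 and equal randomized arms. The plan's own specificity test would show the loss 30%, 85% and over 98% of the time at the larger size, but no text says what such a loss does to the claim.

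**What to change.** Before the arms are compared, state the following:

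1. **Primary contrast.** Pocket on-site provider impression against VIA/VILI impression, with CIN2+ on pathology as the target condition, in the randomized women. Use an unpaired comparison of proportions: each woman has only one of the two examinations (Design & Procedures), so McNemar's test does not apply to this contrast. Say what role, if any, the 550 later Pocket-only women have in it.
2. **Success rule.** Claim better performance only if sensitivity is significantly higher and the 95% confidence interval for the specificity difference excludes a loss larger than a limit fixed in advance.
3. **Order.** Test algorithm against VIA/VILI (also unpaired) only if that claim succeeds, under the same two-part rule.
4. **Everything else.** Report estimates with confidence intervals, without significance claims.

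A single test on sensitivity + specificity − 1 is not a safe substitute, because that index also moves with the threshold. On the curve above, going from 30%/92.7% to 67.9%/67.9% raises it from 0.227 to 0.357 with no gain in discrimination.

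The cost is wording, with no new data or participants. The superiority claim becomes harder to reach, and a specificity limit must be chosen. As a guide to feasibility, if specificity is truly 75% in both arms, the interval's half-width is 1.96 × √(2 × 0.75 × 0.25/422) = 5.8 points. A limit of about 6 points would then be met only about half the time.

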We plan to proceed with prospective enrollment of 550 subjects in the research arm only. Therefore we will no longer have possible randomization into standard of care treatment. The past and newly obtained cervical images will be used to generate the treatment algorithm as described in the objective field (tertiary).

Selection of Subjects

- List inclusion/exclusion criteria and how subjects will be identified.

The subjects will be recruited from 6 different sites in Kenya. No subjects will be recruited/enrolled at DUMC.

Selection of Subjects:

Inclusion Criteria

1. Age \geq 25 years old and \leq 65 years old
2. Sex: Female
3. Positive HPV test within past 6 months
4. HIV+ women

Exclusion Criteria

1. Pregnant women (cannot perform a cervical biopsy on a patient who is pregnant unless absolutely indicated)
2. Women with a negative HPV test
3. Patients incapable of giving informed consent
4. Women with a history of cervical cancer
5. Pelvic exam concerning for cervical cancer or cervical infection

The rationale for the pregnant women exclusion is merely based on standard of care NOT for research. As a general rule, providers do not perform cervical biopsies on pregnant patients unless absolutely needed.

Subject Recruitment and Compensation

- Describe recruitment procedures, including who will introduce the study to potential subjects. Describe how you will ensure that subject selection is equitable and all relevant demographic groups have access to study participation (per 45 CFR 46.111(a) (3)). Include information about approximately how many DUHS subjects will be recruited. If subjects are to be compensated, provide specific prorated amounts to be provided for expenses such as travel and/or lost wages, and/or for inducement to participate.

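### Expert versus algorithm: a two-sided McNemar test with no margin or confidence-interval rule cannot establish that the algorithm is comparable to an expert

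*Combined protocol and SAP*

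**What the plan says.** All the relevant analysis text is in the Data Analysis & Statistical Considerations section of the combined protocol and SAP.

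- **Test.** The plan says that "the two-sided McNemar's test will be used to determine statistically significant differences in specificity and sensitivity for each comparison".
- **Comparison 2.** This is "expert provider interpretation vs. Pocket--algorithm-based results post-study". The Pocket images are to be read at the exam, "by expert colposcopists", and by the algorithm, so expert and algorithm results are paired within women.
- **Hypothesis.** The same sentence gives the purpose of the tests. One part is superiority over VIA/VILI. The other is "and that the automated algorithm performs comparably to an expert".
- **Agreement.** The plan adds that "we will carry out a standard and weighted Kappa to look at the agreement between tests". No threshold or interval is attached.
- **Prevalence.** It expects that "approximately 20% of the patients from each arm will have a CIN2/3 diagnosis".

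No section states a non-inferiority or equivalence margin, a confidence-interval criterion, an alpha level, or a power calculation for this comparison. Under Purpose of the Study, work on the algorithm is a tertiary, retrospective objective that does not guide care.

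**The concern.** McNemar's null hypothesis is that expert and algorithm have equal sensitivity (or specificity). Failing to reject equality is not evidence of similarity. It can mean that the two perform alike, or that there were too few CIN2/3 cases or too many discordant readings to tell. Rejecting equality does not settle the matter either: with several hundred women without CIN2/3, a small specificity difference can be significant and still be unimportant. Without a margin, neither outcome answers whether the algorithm is close enough to the expert.

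At stake is whether a later statement that the algorithm matches an expert would have a rule behind it. No participant's treatment and no primary objective depends on it.

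**Working it through.** The plan gives no power, alpha or effect size for comparison 2, so there is no figure of its own to reproduce. What follows is an illustration.

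**Inputs from the document**
- CIN2/3 prevalence: 20% (Data Analysis & Statistical Considerations). A case is taken as CIN2/3.
- Later enrolment: "We plan to proceed with prospective enrollment of 550 subjects in the research arm only" (Design & Procedures). Cases: 0.20 × 550 = 110; non-cases: 440.
- Randomised part: 1056 women at 1:1 (Design & Procedures), so 1056/2 = 528 in the Pocket arm. Cases: 0.20 × 528 ≈ 106. Pooled with the later women: 528 + 550 = 1078, giving 0.20 × 1078 ≈ 216 cases and 862 non-cases, if all were enrolled and evaluable.
- Subject Recruitment and Compensation gives a total of 400, which does not match the other figures. If all 400 were Pocket women, cases: 0.20 × 400 = 80.

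**Assumptions not in the document**
- Exact two-sided McNemar test, alpha 0.05.
- Discordance ψ of 15%, 20% or 30% between expert and algorithm among cases.
- True sensitivity deficit d = 10 points.

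**Step 1: chance that a real deficit is non-significant.** With n cases, the number of discordant pairs is M ~ Binomial(n, ψ). Given M = m, the number that only the expert detects is B ~ Binomial(m, (ψ + d)/(2ψ)). The exact p-value is min{1, 2·P[Binomial(m, ½) ≤ min(B, m − B)]}. Summing the probability of p > 0.05 over all M and B gives:

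| Cases | ψ = 15% | ψ = 20% | ψ = 30% |
|---|---|---|---|
| 80 (400 women) | 44% | 56% | 71% |
| 110 (550 women) | 25% | 41% | 59% |
| 216 (1078 women) | 3% | 10% | 26% |

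**Step 2: a non-significant result that does not show comparability.** Take 106 cases, with 18 detected only by the expert and 9 only by the algorithm.
- Difference, algorithm minus expert: (9 − 18)/106 = −8.5 points.
- Standard error: √(27 − 9²/106)/106 = 0.048.
- Simple (Wald) 95% CI: −8.5 ± 1.96 × 4.8, or −18.0 to +1.0 points.
- Exact p = 0.12.

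The test does not reject, yet the data are compatible with an 18-point loss of sensitivity.

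**Step 3: a significant result that may not refute comparability.** Take 862 non-cases with 15% discordance, about 129 pairs, split 77 to 52 in the expert's favour.
- Difference: (52 − 77)/862 = −2.9 points.
- McNemar statistic: 25²/129 = 4.84, above the 5% critical value of 3.84.

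The result is significant. Whether 2.9 points matters cannot be said without a margin.

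**Step 4: kappa.** Kappa measures how often two tests agree with each other, not whether they have similar sensitivity and specificity against pathology. The plan gives it no threshold, and applies it to three tests without saying clearly that the expert–algorithm pair is among them.

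**The case against.** Several points on the other side stand.

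- **The plan never says that a non-significant result will be read as comparability.** A reader might infer that it will, because the hypothesis and the test share a sentence. The document does not say so. The fault is a missing decision rule, not a stated wrong one.
- **A reader might infer that no result of this test could support the hypothesis.** That is too strong. If comparable is read as non-inferior, a significant result favouring the algorithm on both sensitivity and specificity would support it.
- **A reader might infer that McNemar is the wrong test for these data.** It is not: both readings come from the same women's images, so the pairing suits it. The mismatch is between a test of difference and a hypothesis of similarity.
- **The illustration rests on assumed discordance, deficit and alpha, and its results run from 3% to 71%.** That is true. The logical point does not need the table, which only shows that the ambiguity could be large.
- **The aim is tertiary.** This lowers the priority. It does not remove the point, because the analysis section states comparability as a hypothesis to be tested.

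The reply that kappa fills the gap does not stand, for the reasons in step 4.

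One further inference goes beyond this point. Since "The past and newly obtained cervical images will be used to generate the treatment algorithm", a reader might conclude that the algorithm will be judged on the images that built it. The document also speaks of testing the algorithm and states no split between development and test images, so that question is open. It is a separate validation matter.

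**Conclusion.** The concern holds in a limited form. For expert versus algorithm, the plan pairs a two-sided test of difference with a hypothesis of comparability and supplies no margin or interval criterion. Non-significance cannot establish comparability, and significance refutes exact equality only. That conclusion rests on the text alone.

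Its practical size depends on the number of evaluable cases, which the document leaves uncertain. Under the stated assumptions, the risk of missing a 10-point deficit is substantial at 80 or 110 cases. It is much smaller at 216, a count that requires every planned Pocket woman to be enrolled and evaluable. Priority is low to modest.

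**What to change.** For comparison 2 only, amend the analysis section along these lines:

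*For the algorithm and the expert reading, the paired differences (algorithm minus expert) in sensitivity and in specificity against pathology will be reported with paired 95% confidence intervals (score or Newcombe paired method). The algorithm will be called comparable, meaning non-inferior, only if both lower limits lie above margins recorded and dated before the comparison is run. If no margins are set, or either limit falls below its margin, the intervals will be reported without that conclusion.*

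The sponsor should choose the margins. Dating them matters because past images are reused and some results may already be known. McNemar may stay beside the intervals, and kappa may stay as description.

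**Cost.** The change is wording plus two margins, but the claim becomes harder to make. With a purely illustrative 10-point margin, no true difference and discordance of 15/20/30%, power for sensitivity is 73/62/47% at 110 cases. Also requiring specificity at the same margin with 440 non-cases gives 73/62/45%. Reaching 80% power for sensitivity needs about 132/166/240 evaluable cases, or 660/830/1200 women at 20% prevalence (cases divided by 0.20). If that is out of reach, reporting the intervals and dropping the conclusion costs almost nothing.

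Held-out images, a fixed algorithm cutoff and a rule for combining expert readings are separate validation points and not part of this change. Nor does it address the VIA/VILI comparisons.
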